7.5.2 Other Secondary endpoints

Other secondary endpoints are exploratory. No correction for multiple hypotheses testing will be made.

- *Composite renal endpoint: Time to first event of chronic dialysis or renal transplant or sustained* reduction of $\geq 40\%$ eGFR (CKD-EPI)_{cr} or*
 - *(for patients with eGFR (CKD-EPI)_{cr} ≥ 30 mL/min/1.73 m² at baseline): sustained eGFR < 15 mL/min/1.73m²*
 - *(for patients with eGFR (CKD-EPI)_{cr} < 30 mL/min/1.73 m² at baseline): sustained eGFR < 10 mL/min/1.73 m²*

*An eGFR (CDK-EPI)_{cr} reduction is considered sustained, if it is determined by two or more consecutive post-baseline central laboratory measurements separated by at least 30 days (first to last of the consecutive eGFR values). If there is no additional measurement ≥ 30 days after the eGFR reduction is observed and the patient dies within 60 days of this measurement, then the eGFR reduction is also considered sustained.

Chronic dialysis is regarded as chronic if the frequency of dialysis is twice or more per week for at least 90 days.

- *Time to first adjudicated HHF*
- *Time to adjudicated CV death*
- *Time to all-cause mortality*
- *Time to onset of DM in patients with baseline pre-DM*

All time-to-event endpoints will be reported in days.

The same model and data frame as used in the primary analysis of primary endpoint will be applied to all these time-to-event endpoints. If the endpoint does not include any cause of death, a CIF plot with all-cause mortality as competing risk will be displayed; otherwise, a CIF plot with causes of death not included in the endpoint as competing risk will be displayed. For all-cause mortality a Kaplan-Meier plot will be displayed.

For time to first HHF and time to CV death, the analysis will be repeated based on investigator defined events. In addition, the analysis of time to CV death will be repeated to include all events up to 7 days prior a reported SARS-CoV-2 infection (based on broad scope SARS-CoV-2 infections)

- *Change from baseline in clinical summary score (HF symptoms and physical limitations domains) of the Kansas City cardiomyopathy Questionnaire (KCCQ) at week 52*

Change from baseline in clinical summary score for HF symptoms and physical limitations domains of the KCCQ at week 52 will be evaluated by a mixed model for repeated measures (MMRM) including LVEF (continuous), age (continuous) and eGFR (CKD-EPI)_{cr} at baseline (continuous) as linear covariates and, baseline score by visit, visit by treatment, sex, geographical region and status of diabetes at baseline as fixed effects. An additional factor of “week reachable” for the parameter in question, which for each patient is the theoretically reachable planned measurement based on the time of randomisation will adjust for the different planned study times.

All on-treatment data up to week 52 will be included and the analysis will be conducted on the treated set.

A sensitivity analysis will be conducted including data after discontinuation (OC-AD) on the randomized set.

An additional analysis will be performed for the Clinical Summary Score on OC-AD without imputing a worst score for patients who die.

- *Occurrence of all-cause hospitalisation (first and recurrent)*

A similar joint frailty model as well as negative binomial regression model as in the HHF will be analysed for all-cause hospitalization. Instead of CV death, all-cause mortality will be jointly modelled as the terminal events in the joint frailty model.

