7.4.1 Primary analysis of the primary endpoint(s)

As the primary endpoint, time to the first event of adjudicated HHF or adjudicated CV death will be reported in days. The primary analysis will be based on RS, using all data available until completion of the planned treatment phase, including the data after end of treatment for patients not completing the treatment phase as planned.

The primary endpoint will be displayed using cumulative incidence function (CIF) curves and expressed as the hazard ratio with associated two-sided 95% confidence intervals (CIs) and two-sided CIs based available alpha-level for the analysis.

For the interim analysis and final analysis, the following Hwang, Shih and De Cani α -spending function at information fraction t_k with parameter $\gamma = -8$ will be used:

$$\alpha^*(\gamma, t_k) = \min \left\{ \alpha, \quad \alpha \frac{1 - e^{-\gamma t_k}}{1 - e^{-\gamma}} \right\} = \min \left\{ 0.025, \quad 0.025 \frac{1 - e^{8t_k}}{1 - e^8} \right\}$$

The alpha levels are expected to be 0.001 and 0.0248 (one-sided) for the interim and final tests respectively, when the interim analysis occurs at the time of 60% information.

Estimator and corresponding confidence intervals will not be corrected for interim analysis.

The primary endpoint will be analysed using Cox regression, with factors of treatment (empagliflozin, placebo), region (North America, Latin America, Europe, Asia and “other” including India, South Africa and Australia), baseline status of diabetes (diabetes, prediabetes, no diabetes), age (continuous), sex, left ventricular ejection fraction (LVEF) (continuous) and eGFR (CKD-EPI)_{cr} at baseline (continuous). Since the stratification factors are included in the model as covariates, no stratified Cox regression will be used.

Breslow’s method will be used for dealing with ties.

The individual relevant components of the composite will be summarized descriptively. In this descriptive analysis of the relevant component for the composite, CV death after HHF will not be counted. In all other analyses of CV death alone defined in this document, all CV deaths will be counted, disregarding any earlier events.

A hierarchical testing procedure will be followed for the assessment of the primary and key secondary endpoints. For all endpoints, superiority of empagliflozin vs. placebo will be evaluated using a two-sided test.

The tests will be performed in the following hierarchical order:

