7.6 FURTHER ENDPOINTS

Time to event endpoints

Further time to event endpoints will generally be analysed in a Cox proportional hazards model similar to the primary analysis on RS. If the endpoint does not include any cause of death, a CIF plot with all-cause mortality as competing risk will be displayed; otherwise, a CIF plot with causes of death not included in the endpoint as competing risk will be displayed.

If there are less than 14 patients with events, then only descriptive statistics will be presented.

Further time to event endpoints are the following:

- Time from first to second adjudicated HHF
- Time to first all-cause hospitalisation
- Time to new onset of atrial fibrillation
- Time to adjudicated MI (fatal or non-fatal)
- Time to adjudicated stroke (fatal or non-fatal)
- Time to adjudicated TIA
- Time to first event of all-cause mortality or all cause hospitalisation
- Time to first event of adjudicated CV death or adjudicated non-fatal MI
- Time to first event of adjudicated CV death or adjudicated non-fatal stroke
- Time to first event of adjudicated CV death, adjudicated non-fatal MI or adjudicated non-fatal stroke (3-point MACE)
- Time to progression to macro albuminuria (defined as UACR >300 mg/g) from baseline for patients with baseline UACR ≤ 300 mg/g
- Time to first new onset of sustained normo- or micro albuminuria (UACR ≤ 300 mg/g) in patients with macro albuminuria at baseline
- Time to first new onset of sustained normo albuminuria (UACR < 30 mg/g) in patients with micro- or macro albuminuria at baseline
- Time to first event of composite renal endpoint¹ or adjudicated CV death
- Time to first event of composite renal endpoint¹, adjudicated CV death or adjudicated HHF
- Time to first event of composite renal endpoint¹ or all-cause mortality

- Time to first acute kidney injury (based on the preferred term)
- Time to non-cardiovascular (non-CV) death (death cases not included in the definition of adjudicated CV death)
- Time to first investigator defined CV hospitalization

¹Composite renal endpoint defined as: *chronic dialysis or renal transplant or sustained* reduction of $\geq 40\%$ eGFR (CKD-EPI)_{cr} or*

- *(for patients with eGFR (CKD-EPI)_{cr} ≥ 30 mL/min/1.73 m² at baseline): sustained eGFR < 15 mL/min/1.73m²*
- *(for patients with eGFR (CKD-EPI)_{cr} < 30 mL/min/1.73 m² at baseline): sustained eGFR < 10 mL/min/1.73 m²*

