9.3 DEFINITION OF DM AT BASELINE

Table 9.3: 1 DM at baseline

Diabetes status at baseline	Definition
T1DM	Patients who fulfil one of the following: 
- investigator-reported medical history of diabetes on the medical history page AND 
- type of diabetes is T1DM
T2DM	Patients who do not have T1DM but fulfil one of the following: 
- investigator-reported medical history of diabetes on the medical history page OR- any pre-treatment HbA1c value ≥ 6.5 OR- stratification via IRT in group of diabetes with either missing assessment of history of diabetes on the medical history page, or no pre-treatment measurement of HbA1c available and investigator reported 'no' for the medical history of diabetes

Table 9.3: 1 DM at baseline (cont.)

Diabetes status at baseline	Definition
Pre-DM	
Patient who fulfil one of the following:
 
- investigator reported ‘no’ for the medical history of diabetes on the medical history page AND no pre-treatment HbA1c ≥ 6.5 and a pre-treatment HbA1c value of ≥ 5.7 and < 6.5 
OR
 
- stratification via IRT in group of pre-diabetes with either
○ missing assessment of history of diabetes on the medical history page and no pre-treatment HbA1c ≥ 6.5 or○ no pre-treatment measurement of HbA1c and investigator reported ‘no’ for the medical history of diabetes 
OR
 
- missing assessment of history of diabetes on the medical history page AND all pre-treatment HbA1c < 6.5 and a pre-treatment HbA1c value of ≥ 5.7 and < 6.5 and stratification via IRT in group of no diabetes
Normal (excluding pre-DM)	Patients not meeting the criteria of DM or pre-DM

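### The Cox models for diabetes onset and for the albuminuria thresholds name no covariate for the baseline value of their own outcome: a modest efficiency loss on exploratory endpoints

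*SAP*

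**What the plan says.** All references are to the current SAP (revision of 12 February 2021).

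- **Diabetes onset.** Section 7.5.2 lists "Time to onset of DM in patients with baseline pre-DM" among the other secondary endpoints, which it calls exploratory, and states: "The same model and data frame as used in the primary analysis of primary endpoint will be applied to all these time-to-event endpoints".
- **The model carried over.** Section 7.4.1 lists treatment, region and "baseline status of diabetes (diabetes, prediabetes, no diabetes), age (continuous), sex, left ventricular ejection fraction (LVEF) (continuous) and eGFR (CKD-EPI)_{cr} at baseline (continuous"). HbA1c and UACR are not among the terms.
- **Albuminuria.** Section 7.6 includes "Time to progression to macro albuminuria (defined as UACR >300 mg/g) from baseline for patients with baseline UACR" at or below 300 mg/g, and two endpoints of sustained regression, to UACR ≤300 mg/g and to <30 mg/g. The rule there is looser: "Further time to event endpoints will generally be analysed in a Cox proportional hazards model similar to the primary analysis on RS". No UACR term is named.
- **Baseline classes.** Table 9.3: 1 places pre-diabetes mainly at HbA1c from 5.7 to below 6.5. One route to type 2 diabetes is "any pre-treatment HbA1c value ≥ 6.5". Some patients are classed as pre-diabetic through the IRT stratum, with "no pre-treatment measurement of HbA1c and investigator reported" absence of a diabetes history.
- **Missing values.** Section 6.6.1 fills a missing continuous Cox covariate with the overall population median. Section 7.6 sets UACR to missing when urine albumin is below quantification.

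**The concern.** A pre-diabetic patient who starts at HbA1c 6.4 is 0.1 from the 6.5 cut-off, and one who starts at 5.7 is 0.8 from it. Restricting the analysis to pre-diabetes leaves that whole spread uncontrolled, and the one glycaemic term in the model cannot vary. The same applies to UACR: patients at 10 and at 290 mg/g are treated alike for crossing 300.

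Elsewhere the SAP adjusts for the endpoint's own baseline. The MMRMs for HbA1c and UACR include baseline by visit, the ANCOVA models include the baseline of the endpoint, and the KCCQ responder models, which are also threshold outcomes, include the baseline of the domain analysed (all Section 7.6). The renal composite has baseline eGFR through the primary model. No reason is given for treating diabetes onset and albuminuria differently.

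Leaving a strong prognostic covariate out of a Cox model moves the hazard ratio toward 1, lowers power and leaves chance imbalance in that covariate uncorrected. What is at stake is the precision of four exploratory results.

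**Working it through.** **1. The plan's own power figure.** Section 9.6 gives 841 events for 90% power at HR 0.80, two-sided 0.05, for the primary endpoint. Schoenfeld: 4 × (1.960 + 1.2816)² / (ln 0.80)² = 42.03 / 0.04979 ≈ 844.1, rounded up to 845. At 841 events, power = Φ(√841/2 × 0.2231 − 1.960) = Φ(1.276) = 89.9%. With the planned interim analysis it is 89.87%, against 89.98% stated. The primary figure reproduces. The SAP states no power for the endpoints discussed here.

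**2. Terms in each model.**

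| Analysis | Own baseline in the model? |
|---|---|
| HbA1c and UACR MMRM (7.6) | Yes, baseline by visit |
| ANCOVA for last on-treatment and follow-up values (7.6) | Yes |
| KCCQ responder logistic models (7.6) | Yes |
| Renal composite Cox model (7.5.2) | Yes, eGFR |
| Diabetes onset Cox model (7.5.2) | No; diabetes factor constant |
| Albuminuria Cox models (7.6) | None named |

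**3. Size, by simulation. Every input is an assumption.** Latent values drift over time and are observed with error at the planned visits from week 12 to week 148. The first qualifying visit is the event (two consecutive visits for the sustained endpoints). Follow-up is 1.0 to 3.2 years. Cox models with Breslow ties were fitted with treatment alone and with treatment plus the observed baseline value, 400 trials per row. Monte Carlo error is about 2 to 3 points.

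Population sizes assumed: 1900 pre-diabetic (33% of the planned 5750); 4900 with UACR ≤300 mg/g; 2000 with UACR ≥30 mg/g; 600 with macroalbuminuria. True HbA1c has mean 5.85 and SD 0.3, with selection on the observed value.

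| Endpoint (within-patient SD) | Events | Power without → with baseline | Gain, points | HR without → with |
|---|---|---|---|---|
| Diabetes onset (0.15) | 11.7% | 24.8 → 30.8% | 6.0 | 0.840 → 0.820 |
| Diabetes onset (0.20) | 16.1% | 48.2 → 51.5% | 3.3 | 0.807 → 0.796 |
| Diabetes onset (0.25) | 21.2% | 62.5 → 66.0% | 3.5 | 0.793 → 0.783 |
| Diabetes onset (0.35) | 32.3% | 79.5 → 81.5% | 2.0 | 0.802 → 0.799 |
| Macroalbuminuria (0.5, log scale) | 5.4% | 33.8 → 42.5% | 8.7 | 0.826 → 0.802 |
| Macroalbuminuria (0.8) | 9.9% | 61.2 → 70.8% | 9.5 | 0.811 → 0.791 |
| Macroalbuminuria (1.0) | 13.8% | 63.2 → 69.0% | 5.7 | 0.841 → 0.826 |
| Sustained normoalbuminuria (0.5 to 1.0) | 16.8 to 30.0% | – | 2.2 to 7.5 | – |
| Macro- to micro- or normoalbuminuria (0.5 to 1.0) | 25.5 to 45.3% | – | 3.8 to 4.7 | – |

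**4. Outer range.** If baseline HbA1c had no measurement error, the gain for diabetes onset would be 10 to 18 points. In a plain proportional-hazards model (600 to 4900 patients, 10 to 50% with events, HR 0.75 to 0.85), the gain depends on the baseline value's hazard ratio per SD: about 0 to 3 points at 1.5, 0 to 9 at 2, 1 to 16 at 3, and 5 to 26 at 4.

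**5. A common scale.** Starting from 80% power, a test statistic larger by a factor r gives power Φ(2.8016 r − 1.960). For r = 1.063, 1.14 and 1.264 the gain is 4.6, 9.1 and 14.3 points.

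**The case against.** **Consequence.** The endpoints are exploratory, no alpha or sample size depends on them, and HbA1c and UACR are also analysed by baseline-adjusted MMRM. One covariate set for all time-to-event endpoints is a defensible choice for consistency. The constant factor does no harm. All of this stands, and it limits the point to efficiency.

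**Wording of 7.6.** The albuminuria model is only generally similar to the primary one, so UACR could still be added. That is true, and the sentence in 7.5.2 does not govern those endpoints. But an open covariate list is better settled before unblinding. The diabetes endpoint has no such latitude.

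**The numbers.** A reader might infer a settled loss of 5 to 20 points. The documents do not support that, since they give no event rate, effect size or prognostic strength. The upper values need a baseline that is very prognostic or measured almost without error. The simulations also compare with a treatment-only model, whereas the SAP model already holds region, age, sex, LVEF and eGFR; information that these share with HbA1c or UACR is credited to the added term. Diabetes onset is taken as HbA1c crossing 6.5. Table 9.3: 1 defines baseline status only, and the endpoint definition is left to the protocol. If investigator report also counts, the link with baseline HbA1c weakens.

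**Bias.** A reader might take the shift in hazard ratio as bias. It largely reflects the difference between a marginal and a conditional hazard ratio, and the unadjusted test is valid.

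**Missing baselines.** A reader might suppose that Section 6.6.1 already covers them. It does not do so adequately. Patients with unquantifiably low albumin have missing UACR, stay at risk for laboratory endpoints under Section 6.8.3, and would receive the median of the whole population.

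**Conclusion.** The point holds as an efficiency weakness. The diabetes-onset model has no HbA1c term and one factor that cannot vary; the albuminuria models name no UACR term. This departs from the SAP's own practice for other endpoints. Eligibility by baseline category uses the baseline value only coarsely.

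Under the stated assumptions, adjustment is worth about 2 to 10 points of power in threshold-crossing scenarios with measurement error: 2 to 6 for diabetes onset, 6 to 10 for macroalbuminuria, 2 to 8 for the sustained regression endpoints. It could be near 0 with a weak or noisy baseline and over 20 with a very strong one. The direction is secure; the size cannot be derived from the documents. Validity, the confirmatory hierarchy and the sample size are unaffected.

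**What to change.** **Section 7.5.2, diabetes onset.** Add baseline HbA1c (continuous, as defined in Section 6.7) to the Cox model and drop the diabetes-status factor. Impute a missing HbA1c from the pre-diabetic set, because an overall median would include patients with diabetes.

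**Section 7.6, albuminuria.** Add log baseline UACR (continuous) to the Cox models for progression to macroalbuminuria and for sustained regression to normo- or microalbuminuria. State a rule that gives patients with urine albumin below quantification a low value, or a separate indicator, in place of the Section 6.6.1 median. This matters mostly for progression, since the regression endpoints start from raised UACR.

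**Cost.** A few sentences of specification and no new data. These hazard ratios will be conditional on a covariate set that differs from the primary model, and the report should say so.

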7.6 FURTHER ENDPOINTS

Time to event endpoints

Further time to event endpoints will generally be analysed in a Cox proportional hazards model similar to the primary analysis on RS. If the endpoint does not include any cause of death, a CIF plot with all-cause mortality as competing risk will be displayed; otherwise, a CIF plot with causes of death not included in the endpoint as competing risk will be displayed.

If there are less than 14 patients with events, then only descriptive statistics will be presented.

Further time to event endpoints are the following:

- Time from first to second adjudicated HHF
- Time to first all-cause hospitalisation
- Time to new onset of atrial fibrillation
- Time to adjudicated MI (fatal or non-fatal)
- Time to adjudicated stroke (fatal or non-fatal)
- Time to adjudicated TIA
- Time to first event of all-cause mortality or all cause hospitalisation
- Time to first event of adjudicated CV death or adjudicated non-fatal MI
- Time to first event of adjudicated CV death or adjudicated non-fatal stroke
- Time to first event of adjudicated CV death, adjudicated non-fatal MI or adjudicated non-fatal stroke (3-point MACE)
- Time to progression to macro albuminuria (defined as UACR >300 mg/g) from baseline for patients with baseline UACR ≤ 300 mg/g
- Time to first new onset of sustained normo- or micro albuminuria (UACR ≤ 300 mg/g) in patients with macro albuminuria at baseline
- Time to first new onset of sustained normo albuminuria (UACR < 30 mg/g) in patients with micro- or macro albuminuria at baseline
- Time to first event of composite renal endpoint¹ or adjudicated CV death
- Time to first event of composite renal endpoint¹, adjudicated CV death or adjudicated HHF
- Time to first event of composite renal endpoint¹ or all-cause mortality

- Time to first acute kidney injury (based on the preferred term)
- Time to non-cardiovascular (non-CV) death (death cases not included in the definition of adjudicated CV death)
- Time to first investigator defined CV hospitalization

¹Composite renal endpoint defined as: *chronic dialysis or renal transplant or sustained* reduction of $\geq 40\%$ eGFR (CKD-EPI)_{cr} or*

- *(for patients with eGFR (CKD-EPI)_{cr} ≥ 30 mL/min/1.73 m² at baseline): sustained eGFR < 15 mL/min/1.73m²*
- *(for patients with eGFR (CKD-EPI)_{cr} < 30 mL/min/1.73 m² at baseline): sustained eGFR < 10 mL/min/1.73 m²*

Chronic dialysis is regarded as chronic if the frequency of dialysis is twice or more per week for at least 90 days.

*An eGFR (CDK-EPI)_{cr} reduction is considered sustained, if it is determined by two or more consecutive post-baseline central laboratory measurements separated by at least 30 days (first to last of the consecutive eGFR values). If there is no additional measurement ≥ 30 days after the eGFR reduction is observed and the patient dies within 60 days of this measurement, then the eGFR reduction is also considered sustained

Continuous endpoints:

The following endpoints will be evaluated by mixed models repeated measures (MMRM) as defined in the protocol.

- HbA_{1c} change from baseline over time (OC-AD on the randomised set and OC-OT on the treated set)
- SBP, DBP change from baseline over time (OC-AD on the randomised set and OC-OT on the treated set)
- Weight change from baseline over time (OC-AD on the randomised set and OC-OT on the treated set)
- NT-pro BNP relative change from baseline over time (OC-AD on the randomised set and OC-OT on the treated set) (value will be transformed to the log scale before MMRM analysis. Estimates obtained from the model will then be back-transformed and reported on the original scale.)
- KCCQ overall summary score change from baseline at week 52 (OC-AD on the randomised set and OC-OT on the treated set) (model will include all timepoints up to week 52)
- KCCQ individual domains change from baseline at week 52 (OC-AD on the randomised set and OC-OT on the treated set) (model will include all timepoints up to week 52)

- KCCQ total symptom score change from baseline at week 52 (OC-AD on the randomised set and OC-OT on the treated set) (model will include all timepoints up to week 52)
- KCCQ based on patient-preferred outcome change from baseline at week 52 (OC-AD on the randomised set and OC-OT on the treated set) (model will include all timepoints up to week 52)
- UACR relative change from baseline over time (OC-AD on the randomised set and OC-OT on the treated set) (value will be transformed to the log scale before MMRM analysis. Estimates obtained from the model will then be back-transformed and reported on the original scale.)
- eGFR (CKD-EPI)_{cr} change from baseline over time (OC-AD on the randomised set and OC-OT on the treated set)

As outlined in the protocol, the above endpoints will be analysed in a mixed model with repeated measures (MMRM), including age, LVEF and eGFR (CKD-EPI)_{cr} at baseline as linear covariates and visit by treatment interaction, baseline by visit interaction, geographical region, sex and status of diabetes at baseline as fixed effects. An additional factor of “week reachable” for the parameter in question, which for each patient is the theoretically reachable planned measurement based on the time of randomisation will adjust for the different planned study times.

An unstructured covariance structure will be used to model the within-patient errors.

Descriptive statistics will be calculated for the value at visit and change from baseline based on OC-AD on the randomised set and OC-OT on the treated set.

Additionally subgroup analyses will be performed as follows:

HbA_{1c} change from baseline will be evaluated by status of diabetes (non-DM, pre-DM, DM).

NTproBNP change from baseline will be evaluated by baseline atrial fibrillation/atrial flutter (as determined by baseline ECG).

UACR will be evaluated by UACR at baseline (<30 mg/g, ≥30mg/g to ≤300mg/g, >300 mg/g).

In order to evaluate the mean effect on eGFR after approximately 3 years, the above described MMRM models will be used in the following way: a mean effect of the timepoints week 124, 148 and 172 will be calculated. Of the three timepoints, only those with at least 5 patients with a measurement at that timepoint will be included in the average calculation. This will be done for the imputations of OC-OT and OC-AD.

For MMRM subgroup analyses, the interaction term treatment-by-visit will be replaced by a treatment-by-subgroup-by-visit interaction term.

To support analysis of renal function, eGFR throughout the trial will be categorized according to the following CKD staging: All calculations for the staging of renal function will be based

on the originally measured laboratory values, not on normalised values with BI standard reference ranges.

Table 7.6: 1 CKD staging

Stage	eGFR (mL/min/1.73m ²)	Description	Label for displays	Additional labels#
1	≥90	Normal or high	≥90	≥90 (CKD 1)
2	60 to <90	Mildly decreased	60 to <90	60 to <90 (CKD 2)
3A	45 to <60	Mildly to moderately decreased	45 to <60	45 to <60 (CKD 3a)
3B	30 to <45	Moderately to severely decreased	30 to <45	30 to <45 (CKD 3b)
4	15 to <30	Severely decreased	15 to <30	15 to <30 (CKD 4)
5	<15	Kidney failure	<15	<15 (CKD 5)

A shift table from baseline to last value on treatment for eGFR (CKD-EPI)_{cr} will be provided.

In cases where urine albumin values are reported to be below the quantification limits (e.g. <3 mg/L) the albumin / creatinine ratio is determined as missing and will not be replaced by estimated values.

Transitions from baseline to last value on-treatment based on the following UACR categories: normal (<30mg/g), microalbuminuria (30-<=300 mg/g and macroalbuminuria (>300 mg/g) will be presented.

For an evaluation of follow-up after discontinuation of trial medication an additional summary of the NT-proBNP, FG, eGFR, UACR, creatinine and the KCCQ endpoints as above will be produced. This summary will include descriptive statistics for baseline, actual values and change from baseline to last on-treatment value and follow-up, and change from last on-treatment assessment to follow-up. The TS-FU patient set will be the basis for this summary, but only those patients with a valid baseline, last value on treatment and follow-up value will be included in all displays. Analyses will be repeated for patients with at least 52 weeks of cumulative exposure (excluding treatment gaps). FG analysis will also be conducted by DM status at baseline (3 categories).

Analyses of change from baseline to LVOT and FU on the TS-FU outlined above will be additionally modelled, separately for LVOT and FU. An analysis of covariance (ANCOVA) model including treatment group, sex, geographical region and status of diabetes at baseline

as fixed effects and baseline eGFR (CKD-EPI)cr (continuous), age (continuous), LVEF (continuous) and baseline of the endpoint (if not already included) as linear covariates will be used.

In addition to the ANCOVA models described above, descriptive statistics will be presented also for creatinine for the value at visit and change from baseline based on OC-AD on the randomised set and OC-OT on the treated set.

In addition to the analyses defined above, KCCQ clinical summary score, clinical symptoms and physical limitations domain will be analysed in two responder analyses (1) defining an increase of 5 points or more from baseline as improvement and (2) defining a reduction of 5 points or more as deterioration.

The frequency and percentage (relative to RS) of patients with improvement as well as the frequency and percentage of patients with deterioration at week 52 will be described. Patients lost to follow-up or who withdrew consent prior week 52 as well as patients who died prior week 52 will be considered as having a deterioration (no improvement) in KCCQ.

Improvement and deterioration will be analysed in separate logistic regression models including treatment, age (continuous), eGFR (CKD-EPI)cr at baseline (continuous), region, sex, baseline LVEF (continuous), status of diabetes at baseline, and baseline value of the KCCQ domain analyzed.

Win ratio:

An unmatched win ratio considering adjudicated CV death and adjudicated HHF will be analysed based on unmatched pairs. All patients randomised to empagliflozin will be compared to all patients randomised to placebo. Only common follow-up time will be considered for the comparison. Patients on empagliflozin are considered to have “won” the comparison if either the other patient has died due to CV causes while the patient on empagliflozin was still alive, or if both patients did not die due to CV causes, then if the other patient had more occurrences of HHF, or if the number of occurrences of HHF is the same but the time to the first occurrence of HHF is longer. The number of comparisons won is noted as N_W . Patients on empagliflozin are considered to have “lost” the comparison if the empagliflozin patient died due to a CV cause while the patient on placebo was still alive, or if both patients did not die due to a CV cause, then if the patient on empagliflozin had more occurrences of HHF, or if the number of occurrences is the same but the time to the first occurrence of HHF is shorter for the empagliflozin patient. The number of comparisons lost is noted as N_L . The win ratio is N_W / N_L .

The rules for winning and losing follow a modified Rogers 2014 [\(8\)](#) approach also considering the time to the first HHF event in case of a tie on the number of HHF events. The analysis of the unmatched win ratio will be conducted as described in Pocock 2012 [\(11\)](#).

Other types of further endpoints

For other types of endpoints e.g. occurrence of adjudicated HHF within 30 days after first adjudicated HHF, change in NYHA class at week 52, HCRU and EQ-5D, descriptive statistics will be provided.

For NYHA class a shift table will also be provided for changes from baseline over time and for change from baseline to last value on treatment and last value in study and worst value in study.

The number of patients shifting from normal (no pre-diabetes) to pre-diabetes or diabetes as well as shifts from pre-diabetes to diabetes will be summarized.

Pharmacokinetic analysis

Descriptive statistics of trough concentrations of empagliflozin will be presented for patients, where PK data is available.

